Version No.	Revision Date	Summary of Changes	Consent Revised Yes/No
1.4	06/14/2021	PI Requested changes as follows: 
 Removal of [name] from the protocol Addition of TKI use for Ph+ and Ph-like B- ALL to eligibility criteria Addition of CMV/EBV serologies to screening procedures 	Yes 
 Added viral serologies to screening procedures
1.3	03/01/2021	PI Requested changes as follows: 
 Physician visits changed to weekly in study calendar and Section 5.2.1 Added additional cycle of blinatumomab for MRD negative subjects that have issues with timing of donor collection on pages Added note that MRD by HTS does not need to be completed within the 14 day window in section 5.1.3 Follow up visits to revised as “weekly in Section 5.4.1 Off study criteria added in Section 5.6.6 Added option of using local lab for MRD by flow since this can be done at CW lab Various administrative changes 	Yes 
 Physician visits revised to weekly Administrative edits
1.2	01/27/2021	Added NGS testing that identifies BOTH B and T cell proteins. Updated under study calendar, section 5.1.3, section 5.3.1 and section 6.2.	No
1.1	10/26/2020	FDA Requested changes as follows: 
 Section 6 revised to add minimal organ functions Section 6.3.5 revised to add a statement referring to Appendix 2 which refers to the current USPI for volume calculations Risk of Serious Adverse Reactions in Pediatric Patients due to Benzyl Alcohol Preservative was added to Section 6.3.7 Blinatumomab AE List in Section 8.3 was revised as per the risks provided by Amgen Appendix 2 revised to add “do not shake” to #3 discussing adding IV solution stabilizer Appendix 2 revised to add a statement for Patients Weighing Under 22 kg Appendix 2 revised to remove all volume calculation tables and refer to the current USPI for preparation 
Local Changes as follows: Removal of [name] from list of Sub-Investigators
	Yes 
 Added “Do not drive, operate heavy machinery, etc. under risks section Added CRS, Neurological problems, and Infections as separate bullets to “Health Risks or Problems” Blina AE list was revised Added drug monograph for dexamethasone

ABSTRACT

Children, adolescents and young adults with relapse or refractory B-acute lymphoblastic leukemia (B-ALL) often have dismal outcomes with chemotherapy alone. Despite allogeneic hematopoietic cell transplantation (HCT) providing a cure for some of these patients, relapse after HCT continues to be the most common reason of treatment failure. Identifying novel ways to improve post-HCT outcomes in these high-risk patients has been challenging and currently no standard approach has been found. We are testing the ability of a biologically active therapy in blinatumomab, an anti-CD19/CD3 bispecific T-cell engager, to further reduce residual leukemia immediately prior to HCT to improve post-HCT outcomes. This Phase 2 study will deliver 1 to 2 cycles of blinatumomab (28-day continuous infusion) in up to 35 subjects with B-ALL that have experienced a relapse or have persistent disease. Subjects will receive blinatumomab immediately prior to proceeding to HCT with best available donor using an alpha/beta T-cell and B-cell depletion preparative transplant regimen.

EXPERIMENTAL DESIGN SCHEMA
Study population: Patients, ages \leq 25 years, with B-ALL meeting study eligibility

STUDY CALENDAR

Drug or Clinical Tests to Be Completed①	Baseline	Days 1 to 28	Days 26 - 30
Screening Assessments [^]	X		
Blinatumomab Cycle 1 and Cycle 2 (if needed)		Continuous infusion	
Clinic Visit - History & Physical Exam		weekly	
Performance Status		weekly	
CBC with differential, CMP*		weekly	
Uric acid, Phosphorus, LDH, PT, PTT, Urinalysis		Day 1	
Disease Evaluation			
Bone Marrow [#] (aspirate and/or Biopsy)	X		X
Lumbar Puncture			X

① Laboratory evaluations will be followed more frequently as clinically indicated

[^] See Section 5.1.3 for screening assessments

*CMP, comprehensive metabolic panel

[#]Bone marrow evaluations will be performed at the end of each cycle of blinatumomab around Day 28 (+/- 2 days) with minimal residual disease (MRD) testing performed using flow cytometry and high-throughput deep sequencing (HTS). Baseline blast samples will be sent for B-cell and T-cell clonality HTS assessment. If T-cell clonal sequences are detected on the baseline sample, T-cell clonality will continue to be sent along with B-cell clonality on subsequent samples.

PROTOCOL SUMMARY

Title	Blinatumomab Bridge to Allogeneic Hematopoietic Cell Transplantation for B-Acute Lymphoblastic Leukemia: A Phase 2 Study
Protocol Short Name	Blinatumomab Bridging Therapy (BBT)
IND Sponsor	N/A
Principal Investigator/ Study Chair/ Coordinating Center/Sponsor- Investigator	[name] Pediatric Clinical Trials Office (CTO) [name]
Study Sites	1) Children's Wisconsin 2) American Family Children's Hospital, Madison WI
Clinical Trial Phase	Phase 2 Study
Study Disease	B-Acute Lymphoblastic Leukemia
Main Eligibility Criteria	
Diagnosis of B-ALL in hematologic complete remission (M1 marrow; < 5% blasts in the bone marrow) by morphology or multi-parameter flow cytometry with evidence of minimal residual disease (MRD) $\geq 0.01\%$ AND that meets one of the following:
 
 Patients in first relapse or greater, OR Patients with very-high risk biology ALL that is proceeding to HCT in first remission (e.g. Induction failure, Severe-hypodiploidy, Ph-like ALL), OR Patients in 1st CR with persistent disease identified as end of consolidation (EOC) MRD $\geq 0.01\%$. 
AND with the intent of going on to an allogeneic hematopoietic cell transplantation (HCT) independent of the study
 
 Patients must have an available donor and have intention of proceeding directly to HCT after completion of 1 to 2 cycles of bridging therapy with blinatumomab. Age ≤ 25 years at time of study enrollment Patients must have fully recovered from the acute toxic effects of all prior chemotherapy, immunotherapy, or radiotherapy prior to entering this study. At least 7 days must have elapsed from prior chemotherapy. Patients who have experienced their relapse after HCT are eligible, provided they have no evidence of acute or chronic graft-versus-host disease (GVHD) and are off all transplant immune suppression therapy for at least 7-days (e.g. steroids, cyclosporine, tacrolimus). Steroid therapy for non-GVHD and/or non-leukemia therapy is acceptable.

Study Rationale	Relapse of childhood B-Acute Lymphoblastic Leukemia (B-ALL) is a vexing clinical problem with high rates of subsequent relapse and death with current treatment approaches. This trial will determine if blinatumomab used as a bridge to allogeneic hematopoietic cell transplantation (HCT) can reduce rates of subsequent relapse and improve survival. If successful, this strategy could become standard of care for patients going to HCT for B-ALL with residual disease.
Primary Objectives	To determine the efficacy of blinatumomab given immediately prior to HCT as “bridging therapy” to eliminate minimal residual disease as measured by Flow Cytometry in children, adolescents, and young adults with relapse or refractory B-ALL.
Secondary Objectives	To compare the results of Flow Cytometry-based versus molecular High-Throughput Deep Sequencing (HTS)-based minimal residual disease (MRD) testing following blinatumomab prior to HCT in children, adolescents, and young adults with relapse or refractory B-ALL and how they correlate with post-HCT outcomes.
Study Design	
This Phase 2 study will determine the effectiveness of delivering 1 to 2 cycles of blinatumomab (Days 1-28) as bridging therapy in children, adolescent and young adults with relapse or persistent MRD B-ALL. Eligible subjects will receive 1 or 2, 28-day cycles of blinatumomab prior to proceeding to HCT. Centralized MRD assessment will be performed after completion of the 28-days of blinatumomab using both flow cytometry (University of Washington, [name] or local lab if applicable) and High-Throughput Deep Sequencing (HTS) MRD technologies (Adaptive Technologies, Seattle, WA). Subjects who achieve flow cytometry negative MRD (<0.01%) after a single cycle of blinatumomab can proceed directly to HCT whereas subjects who remain MRD positive by flow cytometry may receive a 2nd cycle of blinatumomab. Additionally, subjects who achieved MRD negativity after Cycle 1 but are unable to proceed to HCT based on the timing/scheduling of the donor collection, a 2nd cycle of blinatumomab may be given. Subjects who remain MRD positive by flow cytometry after a 2nd cycle of blinatumomab will come off study.
 
This is part one of two-part study. The current study is measuring the timing of blinatumomab in relation to HCT. In the second part of the study, the subjects move on to receive a transplant if eligible.

Study Agent/Intervention Description	Blinatumomab
Number of Subjects	Up to 35 subjects (25 evaluable subjects are needed who are able to proceed to HCT)
Subject Participation Duration	Patients may continue treatment for 1 to 2 cycles of blinatumomab prior to either coming off protocol or proceeding to HCT.
Duration of Follow up	All subjects, including those who discontinue protocol therapy early, will be followed for 30 days from the end of blinatumomab or until the start of the transplant preparative regimen (or other therapy), whichever occurs earlier.

Estimated Time to Complete Enrollment	30 - 36 months
Statistical Methodology	
We will summarize by and compare the subgroups, within the context of a Phase 2 study, of those who are MRD negative by Flow Cytometry (< 0.01%) AND High-Throughput Deep Sequencing (HTS) (MRD undetectable) will be compared to those subjects who are MRD negative by only Flow Cytometry (HTS MRD positive) by demographics and by # of cycles (incomplete, 1 or 2). For comparison of continuous data, we will use a t-test or non-parametric Mann Whitney test, if needed due to distribution. For categorical data we will use a Fisher exact test.
 
Sample Size and Power Estimate
 
It is expected that the study will complete in 30 to 36 months. If there is an 80% rate of MRD negative subjects, a total of 25 evaluable subjects will be recruited. The 95% confidence interval will be (0.59,0.93) with 25 patients. If we must recruit 35 total subjects, we would expect that the proportion will be no less than 0.67 with a 95% CI of (0.47,0.83).
 
We expect ~40% (10 patients) will be MRD negative by HTS (undetectable MRD). With 25 evaluable subjects recruited the 95% CI would be (0.21,0.61).

LIST OF ABBREVIATIONS

AE	adverse event
ALL	acute lymphoblastic leukemia
ALT	Alanine Aminotransferase
ANC	absolute neutrophil count
AST	aspartate aminotransferase
AUC	area under the concentration time curve
BMT	bone marrow transplant
BP	blood pressure
BUN	blood urea nitrogen
CW	Children's Wisconsin
CI	confidence interval
CNS	central nervous system
CR	complete remission
CRF	case report forms
CTCAE	Common Terminology Criteria for Adverse Events
CTEP	Cancer Therapy Evaluation Program
CTMS	Clinical Trials Management System
CTO	Clinical Trials Office
DCTD	Division of Cancer Treatment and Diagnosis
DLT	dose limiting toxicity
DSMC	data safety monitoring committee
DSMP	data safety monitoring plan
ECHO	echocardiogram
FISH	fluorescence in situ hybridization
GVHD	graft versus host disease
HCT	hematopoietic cell transplantation
HSCT	hematopoietic stem cell transplantation
HSV	herpes simplex virus
HTS	high-throughput deep sequencing
IRB	Institutional Review Board
ISO	International Organization for Standardization
LDH	lactate dehydrogenase
MACC Fund Center	Midwest Athletes Against Childhood Cancer Fund Center
MCW	Medical College of Wisconsin
MCWCC DSMC	Medical College of Wisconsin Cancer Center Data Safety Monitoring Committee
MRD	minimal residual disease
MUGA	multi gated acquisition scan
NCI	National Cancer Institute
NGS	Next generation sequencing
NOS	not otherwise specified
OnCore™	Online Enterprise Research Management Environment
ORR	overall response rate
OS	overall survival
PCP	pneumocystis carinii pneumonia
PCR	polymerase chain reaction
Pediatric CTO	Pediatric Cancer/Blood Disorder Clinical Trials Office
PI	principal investigator

PR	partial response
RFS	relapse free survival
SAE	serious adverse event
SRC	Scientific Review Committee
SUSAR	suspected unexpected serious adverse reaction
TRM	transplant related morbidity
ULN	upper limit of normal
UPIRSO	unanticipated problems involving risks to subjects or others
USP	United States Pharmacopeia
WBC	white blood count

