2.3 Secondary Objectives

To compare the results of Flow Cytometry-based versus molecular High-Throughput Deep Sequencing-based minimal residual disease (MRD) testing following blinatumomab prior to HCT in children, adolescents and young adults with relapse or persistent MRD B-ALL and how these MRD correlate with post-HCT outcomes.

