9.2 Bone Marrow Response Criteria

Complete Remission, MRD Negative (CR MRD)

- A bone marrow with < 5% blasts by morphology (hematologic complete remission);
AND
- MRD < 0.01% by flow;
AND
- No evidence of circulating blasts or extramedullary disease;
AND
- Recovery of peripheral counts (ANC > 500/ μ L and PLT count > 50,000 μ L).
- Qualifying marrow and peripheral counts should be performed within 1 week of each other

Complete Remission (CR)

- A bone marrow with < 5% blasts by morphology (hematologic complete remission);
AND
- No evidence of circulating blasts or extramedullary disease;
AND
- Recovery of peripheral counts (ANC > 500/ μ L and PLT count > 50,000 μ L).
- Qualifying marrow and peripheral counts should be performed within 1 week of each other.

Complete Response with Incomplete Count Recovery (CRi)

- A bone marrow with < 5% blasts by morphology (hematologic complete remission); **AND**
- No evidence of circulating blasts or extramedullary disease; **AND**
- Insufficient recovery of absolute neutrophil counts (ANC < 500/ μ L), and or insufficient recovery of platelets (PLT counts < 50,000/ μ l),

Partial Remission (PR)

- Complete disappearance of circulating blasts and one of the following:
- A decrease of at least 50% of blasts in the bone marrow with > 5% and \leq 20% blasts by morphology with recovery of peripheral counts (ANC > 500/ μ L and PLT count > 50,000 μ L)

Note: only patients who entered the study with \geq 20% blasts in the marrow may be assessed as PR

Stable Disease (SD)

Patient does not satisfy the criterion for either CR, CRi, PR or disease progression.

Progressive Disease (PD)

An increase of at least 25% in the absolute number of bone marrow or circulating leukemic cells, development of new sites of extramedullary disease, or other laboratory or clinical evidence of progression of disease.

Not Evaluable (NE)

Aplastic or severely hypoplastic marrow without any blast percentage. Bone marrow aplasia/hypoplasia is defined as overall marrow cellularity less than 10-20%. In this instance, marrow evaluation should be repeated every 1-2 weeks until response determination can be made.

Relapse

After documentation of remission, one bone marrow aspirate and/or biopsy showing \geq 5% leukemic blasts or pathological evidence of extramedullary disease.

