10.1.2 Secondary Efficacy Variables

- The percent of subjects that remain in CR, achieve MRD negative by Flow Cytometry ($< 0.01\%$) and by molecular High-Throughput Deep Sequencing (HTS-MRD negative) (MRD undetectable) (Adaptive Technologies, Seattle, WA) after completion of 1 to 2 cycles of Blinatumomab.

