10.7.3 Secondary Analysis (or Analysis of Secondary Endpoints)

10.7.3.1 Secondary Endpoints

- The proportion who are HTS-MRD negative (MRD undetectable) will be summarized with 95% CI.

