10.7.4 Other Analyses/Assessments

We will summarize by and compare the subgroups of those who are MRD negative by Flow Cytometry AND HTS will be compared to those subjects who are MRD negative by only Flow Cytometry (HTS MRD positive) by demographics and by # of cycles (incomplete, 1 or 2). For comparison of continuous data, we will use a t-test or non-parametric Mann Whitney test, if needed due to distribution. For categorical data we will use a Fisher exact test.

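### The planned flow-versus-HTS contrast cannot separate a difference in cut-off from a difference in assay; a paired table at a common 0.01% cut would help address the secondary objective at little cost

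*Combined protocol and SAP*

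**What the plan says.** The first half of the secondary objective (Section 2.3, and in similar terms in the Protocol Summary) is "To compare the results of Flow Cytometry-based versus molecular High-Throughput Deep Sequencing-based minimal residual disease (MRD) testing following blinatumomab prior to HCT".

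The two assays have different rules for a negative result:

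- **Flow.** Section 9.2 requires "MRD < 0.01% by flow", and Sections 10.1.1 and 10.7.2 use the same level.
- **HTS.** Section 10.7.3.1 states "The proportion who are HTS-MRD negative (MRD undetectable) will be summarized with 95% CI". Sections 10.1.2 and 10.3.1 use the same rule. No numeric level is attached to it.

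The only contrast involving both assays is in the Statistical Methodology row of the Protocol Summary and in Section 10.7.4. Double-negative subjects, in the Protocol Summary's words "MRD negative by Flow Cytometry (< 0.01%) AND High-Throughput Deep Sequencing (HTS) (MRD undetectable", are compared with "those subjects who are MRD negative by only Flow Cytometry (HTS MRD positive) by demographics and by # of cycles", using a t-test, Mann-Whitney test or Fisher's exact test. The secondary efficacy variable in Section 10.1.2 is a joint condition: remission, flow-negative and HTS-negative.

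The documents do not plan a paired flow-by-HTS table, a reading of HTS at 0.01%, or a comparison of levels. They give no detection limit for either assay. Section 10.7.1 collects both measures at the end of each cycle but does not say whether they are recorded as numbers or as categories.

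**The concern.** Suppose both assays read 0.005% on the same marrow. They agree exactly, yet the subject is counted as flow-negative and HTS-positive. The flow-only-negative group can therefore hold two kinds of subject: those in whom HTS reads 0.01% or more, where the assays disagree at the same level, and those in whom HTS detects something below 0.01%, where they may or may not disagree. Nothing planned tells them apart.

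Both arms of the specified contrast are also flow-negative. Within it HTS can only find as much disease as flow or more, and the flow-positive/HTS-negative cell never appears. The joint variable in Section 10.1.2 likewise cannot exceed the flow-negative rate.

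What is at stake is whether the trial can say anything about the assays themselves, as its secondary objective asks, rather than only about two decision rules set at different levels.

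**Working it through.** **Inputs.** From Section 10.3.1: 25 evaluable subjects, an 80% flow-negative rate, and about 40% (10 patients) HTS-negative. The cut-offs are those listed above. One assumption is not in the documents: every HTS-negative subject is also flow-negative. The distribution of HTS levels and both detection limits are unknown, so results are given as ranges.

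**Step 1: reproduce the plan's figures.** 0.80 × 25 = 20 and 0.40 × 25 = 10. The exact (Clopper-Pearson) 95% limits are Beta(0.025; x, n − x + 1) and Beta(0.975; x + 1, n − x).

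- 20/25 gives (0.593, 0.932); the plan prints (0.59, 0.93).
- 10/25 gives (0.211, 0.613); the plan prints (0.21, 0.61).

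Both match, so reading the expectations as 20 and 10 of 25 fits the plan's own intervals.

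**Step 2: the table on the printed definitions.**

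| | HTS undetectable | HTS detected | Total |
|---|---|---|---|
| Flow < 0.01% | 10 | 20 − 10 = 10 | 20 |
| Flow ≥ 0.01% | 0 (assumed) | 5 | 5 |

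Section 10.7.4 uses only the first row. Ten of the 20 flow-negative subjects (50%; 40% of all 25) are HTS-positive.

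**Step 3: the same subjects at a common 0.01% cut.** Let a be the number of the 10 flow-negative/HTS-positive subjects whose HTS level is 0.01% or more. Let b be the number of the 5 flow-positive subjects whose HTS level is detectable but below 0.01%.

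| | HTS < 0.01% | HTS ≥ 0.01% |
|---|---|---|
| Flow < 0.01% | 10 + (10 − a) | a |
| Flow ≥ 0.01% | b | 5 − b |

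Discordant subjects = a + b, with 0 ≤ a ≤ 10 and 0 ≤ b ≤ 5. The total runs from 0 to 15 of 25 (0% to 60%). Even the direction is open: a = 0 and b = 5 would put all the discordance on the side of flow reading higher.

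**Step 4: how far the cut-off alone can go.** As an illustration, assume both assays return identical readings, flow can read below 0.01%, and k of 25 subjects have detectable disease below 0.01%. At the common cut both assays give 20/25 negative, with no discordance. On the printed definitions HTS-negative is (20 − k)/25:

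| k | HTS-negative | Exact 95% CI | Discordance |
|---|---|---|---|
| 2 | 18/25 | (0.51, 0.88) | 2 to 0 |
| 5 | 15/25 | (0.39, 0.79) | 5 to 0 |
| 10 | 10/25 | (0.21, 0.61) | 10 to 0 |

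The plan includes no McNemar test. If one were run, its exact p-value would be 2 × 0.5^k: 0.0625 at k = 5, 0.031 at k = 6 and 0.002 at k = 10, with no assay difference at all.

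**Step 5: sensitivity to the meaning of 25.** Sections 3.2 and 10.2 describe the 25 evaluable subjects as flow-negative. On that reading the flow-only-negative group would be 25 − 10 = 15, not 10. The sizes change; the argument does not.

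**The case against.** The strongest reply is that the asymmetry is intended. Section 3.1 uses exactly these two rules to separate the conditioning groups, and Section 1.2 gives the reason: HTS status before transplant predicted relapse better than flow. Asking how *flow below 0.01%* and *HTS undetectable* compare as decision rules is legitimate, and the definitions are stated consistently. This stands. The definitions are not a drafting error and need not change.

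Second, the contrast in Section 10.7.4 is a subgroup description. It does not test which assay finds more disease, and the plan nowhere commits to crediting the gap to the technology. This also stands. The weakness lies between the objective and the analysis, since nothing else specified compares the assays.

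Third, if flow cannot read below 0.01%, an HTS result there is a real sensitivity gain. This stands too. Neither detection limit is given, and flow may be run at a local laboratory (Sections 3.1 and 10.1.1), so the limit may also vary.

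A reader might go further and infer that the HTS excess is an artefact, that the share due to the assay is bounded by the 10 flow-negative/HTS-positive subjects, or that every statement about one assay finding more disease must rest on the common cut. The documents support none of these. The first needs a flow detection limit they do not give. The second overlooks the 5 flow-positive subjects, and also that the whole gap could be an assay effect even if every HTS value lay below 0.01%. The third is a preference that would set aside the low-level detection for which HTS is used.

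**Conclusion.** The point holds as a gap between objective and analysis. The plan sets out to compare two assays but specifies only a contrast within flow-negative subjects, under rules set at different levels, and that contrast cannot divide the gap between cut-off and assay. On the plan's expectations the gap is 10 of 25 subjects, and total discordance at a common 0.01% cut could be 0 to 15 of 25. The documents do not narrow that range.

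These sizes rest on reading the expectations as 20/25 and 10/25 and on every HTS-negative subject being flow-negative. The primary endpoint, its interval, the sample size and the two-stage rule use flow only and are unaffected. It would be too strong to say that the secondary objective is uninterpretable: the contrast can be read for what it is, flow below 0.01% against HTS undetectable. This is a cheap improvement, not a condition for a valid trial.

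**What to change.** Keep the planned groups and both definitions of negativity. In the Statistical Methodology row of the Protocol Summary and in Section 10.7.4:

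1. Add a descriptive, paired four-cell flow-by-HTS table for all assessed subjects, including the flow-positive ones, with both assays cut at 0.01%. Place it beside the same table on the printed definitions, and state which end-of-cycle sample supplies the pair.
2. Split the flow-negative/HTS-positive subjects into HTS detectable but below 0.01% and HTS at 0.01% or more.
3. Record the numeric level and the detection limit for both assays, including flow run at a local laboratory.
4. Label the existing contrast *flow < 0.01% versus HTS undetectable*.

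The cost is a few lines of analysis text and two small tables. If the case report form does not already capture numeric levels, which Section 10.7.1 leaves open, it needs the extra fields, preferably before results are seen. The cells will be small, so the tables should stay descriptive.
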